4.1. Primary Objective

The primary objective of this study is to evaluate the safety and tolerability of abemaciclib in Chinese patients with advanced and/or metastatic cancers.

4.2. Secondary Objectives

The secondary objectives of this study are:

- to assess the PK of abemaciclib and its metabolites in Chinese patients with advanced and/or metastatic cancers
- to assess the antitumor activity of abemaciclib

[figure not shown]
5. Study Design

5.1. Summary of Study Design

This study is a multicenter, open-label, Phase 1 trial of abemaciclib in Chinese patients with advanced and/or metastatic cancers.

The study will be focused on safety evaluation and PK data collection in patients with all advanced and/or metastatic cancers. Patients will be randomized into 2 dose cohorts, and orally receive abemaciclib 150 mg or 200 mg every 12 hours (Q12H). One cycle is defined as 28 days (Cycle 1: 32 days), with modifications during Cycle 1 to enable PK sampling following a single dose and repeated doses. The treatment of abemaciclib will continue until disease progression, development of unacceptable toxicity, or fulfillment of the other discontinuation criteria. In case of patient discontinuation during Cycle 1, the enrollment will be extended until at least 10 patients with completed PK data accrued in each cohort. Analysis on available PK and safety data will be conducted after study completion.

All patients in the study receive at least 2 cycles of abemaciclib unless one or more of the criteria for discontinuation (refer to Protocol Section 6.3.1) are fulfilled; the short-term follow-up period for poststudy evaluation is 30 ± 7 days after the decision to discontinue treatment. [Figure JPBR 5.1](#) shows the study design for Study JPBR.

Abbreviations: Q12H = every 12 hours; R = randomization.

Figure JPBR 5.1 Study design for JPBR.

5.2. Determination of Sample Size

There are no formal sample size calculations. Twenty or more patients may be enrolled to ensure 10 completers (that is, obtained the full set of PK samples for appropriate PK evaluation) in each dose cohort.

5.3. Method of Assignment to Treatment

Patients who meet all criteria for enrollment will be assigned to receive abemaciclib in this study. Before each patient's enrollment into the study, an eligibility check must be conducted at the investigational site to confirm that each patient meets all enrollment criteria. Upon confirmation

of eligibility, the sponsor will confirm the dose and identification number assignment for each patient using the interactive web response system (IWRS).

Upon obtaining informed consent, site personnel should access the IWRS, which will enter a patient number. Patients who meet all criteria for enrollment will be randomly assigned to receive either 150-mg or 200-mg abemaciclib. A simple randomization method will be adopted. Assignment to treatment groups will be determined by a computer-generated random sequence using the IWRS. Site personnel will confirm that they have located the correct dosage by entering a confirmation number found on the packages into the IWRS.

6. A Priori Statistical Methods

6.1. General Considerations

Statistical analysis of this study will be the responsibility of Eli Lilly and Company. The analyses for this study will be descriptive, except for possible efficacy analysis as deemed appropriate. Exploratory analyses of the data will be conducted as deemed appropriate.

Safety analyses and all efficacy analyses will be conducted using the treated analysis set, which will include the data from all patients who randomized and received at least one dose of any study drug.

Data analyses will be provided by cohort, and for all study patients combined wherever appropriate. For continuous variables, summary statistics will include number of patients, mean, median, standard deviation, minimum, and maximum. Categorical endpoints will be summarized using number of patients, frequency, and percentages.

6.2. Adjustments for Covariates

No adjustments for covariates.

6.3. Handling of Dropouts or Missing Data

Missing data will not be imputed.

6.4. Multiple Comparisons/Multiplicity

No adjustments for multiplicity.

6.5. Use of an “Efficacy Subset” of Patients

Not applicable.

6.6. Patient Disposition

A detailed description of patient disposition will be provided. It will include a summary of the number and percentage of patients entered into the study, enrolled in the study, reasons for discontinuation from study treatment, and reasons for discontinuation from the study. Reason for discontinuation from both study treatment and the study will be listed by the pre-determined categories. If the reason for discontinuation is adverse event (AE) or death, the associated AE or cause of death will be reported. All patients entered in the study will be included in the summary.

6.7. Patient Characteristics

Patient characteristics will include the analysis of the following:

- Patient demographics will be reported
- Baseline disease characteristics
- Prior disease-related therapies.

Patient demographics and baseline disease characteristics will be listed for all patients on therapy and summarized by cohort. Patient demographics will include sex, race, age, height, weight, and body mass index (BMI). Baseline disease characteristics will include initial pathological diagnosis and Eastern Cooperative Oncology Group (ECOG) performance status.

Prior systemic therapy, radiotherapy, and surgeries will be listed and summarized for all patients on therapy.

Other patient characteristics will be analyzed as deemed appropriate.

6.8. Treatment Compliance

Treatment compliance of abemaciclib will be measured by capsule counts and summarized over the whole treatment period. Compliance will be calculated as the ratio of total dose taken to the total assigned dose (minus any dose adjustments and doses omitted/withheld for medical or logistical reasons). The total assigned dose for a patient with no adjustments, omissions, or extensions for logistical reasons is $150 \text{ mg per dose} \times 2 \text{ doses per day} \times 28 \text{ days} = 8400 \text{ mg}$ for lower dose cohort and $200 \text{ mg per dose} \times 2 \text{ doses per day} \times 28 \text{ days} = 11200 \text{ mg}$ for higher dose cohort.

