6.12. Safety Analyses

6.12.1. Extent of Exposure

The number of cycles of treatment received, dose delays, and dose intensity will be summarized.

Extent of exposure will be measured by pill counts and summarized by cycle. The summary will include total dosage taken and dose intensity. Dose intensity will be calculated as the ratio of total dose taken to the assigned cumulative dose. The assigned cumulative dose for each patient during each cycle is 150 mg per dose \times 2 doses per day \times 28 days = 8400 mg for lower dose cohort and 200 mg per dose \times 2 doses per day \times 28 days = 11200 mg for the higher dose cohort. The assigned cumulative dose while on study for lower and higher dose cohort is 2×150 mg \times number of days and 2×200 mg \times number of days on treatment, accordingly.

Dose adjustments including the reasons for dose adjustment will also be listed and summarized.

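### SAP Section 6.8 divides the dose taken over the whole treatment period by the assigned dose of one 28-day cycle, so full adherence scores about 200% after two cycles and 100 points more per further cycle.

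*SAP*

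**What the plan says.** Section 6.8 sets the period: "Treatment compliance of abemaciclib will be measured by capsule counts and summarized over the whole treatment period". Compliance is total dose taken divided by total assigned dose, and the assigned dose is reduced as follows: "minus any dose adjustments and doses omitted/withheld for medical or logistical reasons". The section then gives the denominator: "The total assigned dose for a patient with no adjustments, omissions, or extensions for logistical reasons is" 150 × 2 × 28 = 8400 mg in the lower cohort and 200 × 2 × 28 = 11200 mg in the higher. It attaches no per-cycle label and no multiplier for cycles or days.

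Section 5.1 describes the duration of treatment: "All patients in the study receive at least 2 cycles of abemaciclib", unless a discontinuation criterion is met, and "The treatment of abemaciclib will continue until disease progression, development of unacceptable toxicity, or fulfillment of the other discontinuation criteria". On cycle length it says: "One cycle is defined as 28 days (Cycle 1: 32 days), with modifications during Cycle 1 to enable PK sampling following a single dose".

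Section 6.12.1 uses the same two amounts for dose intensity, but with a unit: "The assigned cumulative dose for each patient during each cycle is 150 mg per dose", and so on to 8400 mg, with 11200 mg for the higher cohort. It reports exposure cycle by cycle ("Extent of exposure will be measured by pill counts and summarized by cycle") and gives a separate on-study denominator of 2 × 150 mg or 2 × 200 mg times the number of days on treatment.

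**The concern.** A compliance ratio is interpretable only if both halves cover the same period. In Section 6.8 the numerator grows with every cycle while the denominator stays at one cycle's worth. Section 6.12.1 confirms that 8400 and 11200 mg are one-cycle amounts, because it labels them that way and uses a different formula for the whole time on study.

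The resulting table could not separate adherent from non-adherent patients. If the cohorts differ in cycles received or in doses withheld, their compliance figures would differ even with identical adherence. Safety and tolerability are the primary objective, and compliance is part of the context for reading those data by cohort.

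A smaller question concerns Section 6.12.1. It applies the 28-day amount to every cycle although Cycle 1 lasts 32 days, and it does not say whether days on treatment means calendar days or dosing days.

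**Working it through.** **Inputs.** Dose per administration is 150 or 200 mg, two doses per day, 28 days (Section 6.8). A cycle is 28 days, with Cycle 1 at 32 days, and at least two cycles are planned (Section 5.1). The number of doses assigned in Cycle 1 is not in the SAP, so three layouts are assumed: 56 doses (28 twice-daily days), 57 doses (one single dose plus 28 twice-daily days) and 64 doses (32 twice-daily days). The last is an outer bound, since Section 5.1 says that Cycle 1 is modified for single-dose sampling.

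**The plan's own figures.** 150 × 2 × 28 = 8400 and 200 × 2 × 28 = 11200. Both products are correct; each equals 56 doses.

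**Compliance as written.** Let D1 be the doses assigned in Cycle 1, k the number of cycles and a the fraction of scheduled doses taken:

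compliance = a × [D1 + 56(k − 1)] / 56

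The mg per dose cancels, so both cohorts give the same ratios.

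| Patient | k | D1 = 56 | D1 = 57 | D1 = 64 |
|---|---|---|---|---|
| a = 1 | 2 | 112/56 = 200% | 113/56 = 201.8% | 120/56 = 214.3% |
| a = 1 | 4 | 224/56 = 400% | 225/56 = 401.8% | 232/56 = 414.3% |
| a = 1 | 6 | 336/56 = 600% | 337/56 = 601.8% | 344/56 = 614.3% |
| a = 0.5 | 2 | 56/56 = 100% | 56.5/56 = 100.9% | 60/56 = 107.1% |
| a = 0.5 | 4 | 112/56 = 200% | 112.5/56 = 200.9% | 116/56 = 207.1% |

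Each further cycle adds 56/56 = 100 points at full adherence under any layout.

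**Effect of the subtraction clause.** Suppose 14 days of doses (28 doses) are withheld for medical reasons and every other dose is taken. If the deduction is made from the stated 56 doses, the denominator is 56 − 28 = 28 doses.

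- Two cycles: (112 − 28)/28 = 300% to (120 − 28)/28 = 328.6%.
- Six cycles: (336 − 28)/28 = 1100% to (344 − 28)/28 = 1128.6%.
- With 28 days withheld, the denominator is 56 − 56 = 0 and the ratio is undefined.

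**With matching periods.** Over two cycles with 56 doses each, the assigned dose is 16800 mg (lower cohort) or 22400 mg (higher cohort), and full adherence scores 100%. The same holds for any k.

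**Section 6.12.1, Cycle 1.** If days on treatment are calendar days, the 32-day amounts are 2 × 150 × 32 = 9600 mg and 2 × 200 × 32 = 12800 mg, against per-cycle amounts of 8400 and 11200 mg. If they are dosing days and Cycle 1 has 28 of them, there is no gap. The choice matters if this formula is borrowed for Section 6.8. On calendar days the two-cycle denominator in the lower cohort is 2 × 150 × 60 = 18000 mg, so a fully adherent patient with 56 doses per cycle scores 16800/18000 = 93.3%.

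**The case against.** The strongest reply is that Section 6.8 is under-specified rather than wrong. It could be read as a ratio on a 28-day unit that is then summarized over treatment. Section 5.1 makes 28 days the cycle length, Section 6.12.1 labels the same amounts per cycle, and the mention of logistical extensions fits a fixed unit better than an open-ended course. On that reading the two halves match, and a programmer would probably never produce a 600% table.

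That may well be the intention, but the reading needs a unit that Section 6.8 does not state. The section names the whole treatment period, calls the amount the total assigned dose and does not refer to Section 6.12.1. Planned later cycles are scheduled treatment, not logistical extensions. Section 3 lists the compliance analysis among the items clarified in Version 2, so this is the considered text.

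Parts of the objection stand:

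- Both products are correct; the error lies in how they are used.
- Section 6.8 gives 8400 and 11200 mg only for a patient without adjustments or omissions, so the withheld-dose figures rest on the inference that deductions start from those amounts.
- The 64-dose layout sits poorly with the single-dose sampling in Cycle 1, so the upper ends of the ranges deserve little weight.
- The Section 6.12.1 point is conditional, because the Cycle 1 calendar belongs to the protocol, which is not at hand.

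The main conclusion needs none of these.

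**Conclusion.** The concern holds. The compliance rule in Section 6.8 sets a whole-period numerator against a one-cycle denominator and gives a wrong result for any patient treated beyond one cycle. At full adherence the score is about 200% after two cycles (200% to 214% over the assumed Cycle 1 layouts), with exactly 100 points more for each further cycle. The subtraction clause makes the distortion worse.

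This should be fixed, but its reach is limited. Only descriptive compliance tables are affected, and no primary safety or PK result depends on the ratio. The on-study dose intensity in Section 6.12.1 does not share the error, because its denominator scales with days. The Cycle 1 discrepancy there arises only if days are calendar days, and is a matter for clarification.

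**What to change.** In Section 6.8, define the total assigned dose as the sum of protocol-scheduled doses over all cycles the patient was treated, less the adjusted, omitted and withheld doses already listed. Numerator and denominator then cover the same period. If 8400 and 11200 mg are kept, label them as the amount for one 28-day cycle.

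In Section 6.12.1, take the Cycle 1 denominator from the protocol's actual Cycle 1 schedule and define days on treatment to match it. Section 6.8 can then use the same convention. Sections 5.1, 6.8 and 6.12.1 must be reconciled on this point.

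The cost is SAP wording and derivation code. No new data are needed.

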6.9. Concomitant Therapy

All medications will be coded to the generic preferred name according to the current World Health Organization (WHO) drug dictionary. All concomitant medications will be listed and summarized using the preferred name for all patients on therapy by cohort.

6.10. Efficacy Analyses

The study was not designed to make an efficacy assessment. However, tumor response data, progression-free survival (PFS) data and overall survival (OS) data will be analyzed. Tumor response and progression will be evaluated using the Response Evaluation Criteria in Solid Tumors (RECIST v1.1, Eisenhauer et al. 2009).

Reported lesion data (target/ non-target or measurable/ nonmeasurable) will be listed for all enrolled patients. Change from baseline in the sum of target lesion size will be listed by cycle and depicted as a waterfall plot. The waterfall plot will depict each patient's best change from baseline in the sum of target lesion size while on study.

Investigator-determined response by cycle and best overall response for each patient will be listed. Response will be summarized using the Overall Response Rate (ORR) and Disease Control Rate (DCR). Overall Response Rate will be defined as the percentage of enrolled patients with a best response of partial response (PR) or complete response (CR). Disease Control Rate will be defined as the percentage of enrolled patients with a best response of PR, CR, or stable disease (SD). Exact 95% confidence intervals (CIs) for each of these measures will be calculated.

Progression-free survival (PFS) time will be measured from the date of the first dose to the date of investigator-determined objective progression as defined by RECIST v1.1, or death from any

cause. If a patient is not known to have progressed or died at the time of analysis, PFS time will be censored at the last known progression-free assessment. The detailed censoring rules are described in the table below (Table JPBR.6.1). PFS for each patient will be calculated and listed. Swimmer plot will be applied to present the time to event for each patient.

Table JPBR.6.1. Rules for Determining Date of Progression or Censor for Progression-Free Survival

Rule	Situation	Date of Progression or Censor	Outcome
1	No baseline tumor assessments	Date of first dose	Censored
2	No post baseline assessments and no death	Date of first dose	Censored
3	No documented progression and no death (with a post-baseline tumor assessment)	Date of last adequate tumor assessment	Censored
4	Patient lost to follow-up (or withdrew consent from study participation) before documented progression or death	Date of last adequate tumor assessment	Censored
5	Documented progression	Date of documented progression. If a tumor assessment was done on multiple days, use the earliest date for that visit.	Progressed
6	Death without documented progression	Date of death	Progressed
7	Documented progression or death after missing ≥ 2 consecutive post-baseline tumor assessments	Date of last adequate tumor assessment before missed assessments or date of first dose, whichever is later	Censored

Note: Progression-free survival and associated outcome is determined by the earliest of the dates above, if more than 1 situation applies.

Overall survival (OS) duration will be measured from the date of the first dose to the date of death from any cause. For each patient who is not known to have died, OS will be censored at the date of last day known alive.

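### PFS censoring Rule 4 has no floor at first dose, so a patient lost or withdrawn before any post-baseline scan could be given a negative PFS time if the baseline scan counts as an adequate assessment

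*SAP*

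**What the plan says.** All of this is in SAP section 6.10 and its Table JPBR.6.1.

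- **Time origin:** "Progression-free survival (PFS) time will be measured from the date of the first dose to the date of investigator-determined objective progression", with death from any cause also an event.
- **Rule 2:** the situation is "No post baseline assessments and no death". The patient is censored at first dose.
- **Rule 3:** the situation is "No documented progression and no death (with a post-baseline tumor assessment"). The patient is censored at the last adequate assessment.
- **Rule 4:** the situation is "Patient lost to follow-up (or withdrew consent from study participation) before documented progression or death". The date is "Date of last adequate tumor assessment", with no further condition.
- **Rule 6:** death without documented progression is an event on the date of death.
- **Rule 7** (progression or death after two or more consecutive missed assessments): the date is "Date of last adequate tumor assessment before missed assessments or date of first dose, whichever is later".
- **Note to the table:** "Progression-free survival and associated outcome is determined by the earliest of the dates above, if more than 1 situation applies".
- **Use of the result:** "PFS for each patient will be calculated and listed", and a swimmer plot is drawn.

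**The concern.** Rules 3, 4 and 7 all censor at a last adequate assessment. Rule 3 protects against a date before the time origin by requiring a post-baseline scan. Rule 7 does so by taking first dose if that is later. Rule 4 does neither.

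The patient at issue has a baseline scan before first dose, takes at least one dose, and is then lost or withdraws from the study before any further scan. Rules 2 and 4 both describe this patient and give different dates. One might expect Rule 2, the more specific rule, to prevail, but the note says that the earliest date does. At stake is whether the table, applied as written, gives a PFS time that cannot exist. A programmer would then have either to report it or to override the SAP without documented authority. Section 3 says that Version 2 was written partly to clarify the PFS and OS censoring rules, so the table ought to be usable as it stands.

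**Working it through.** The SAP states no figure to reproduce. The check is to apply the table to one patient.

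**Inputs**
- First dose = day 0 (section 6.10, PFS origin).
- Baseline scan on day -b. The SAP gives no screening window, so b from 0 to 28 days is an assumption.
- No post-baseline scan; lost or consent withdrawn; not known to have died.
- The baseline scan is taken to be an adequate assessment (an assumption, discussed under the objection).

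**Which rules apply**
- Rule 1 does not: there is a baseline scan.
- Rule 2 does: date = 0.
- Rule 3 does not: there is no post-baseline scan.
- Rule 4 does: date = -b.
- Rules 5 to 7 do not: there is no progression and no death.

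**Note applied:** date = min(0, -b) = -b. PFS is the censoring date minus the first-dose date.

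| b (days, assumed) | Rule 2 | Rule 4 | Note: earliest | Rule 4 floored at first dose |
|---|---|---|---|---|
| 0 | 0 | 0 | 0 | 0 |
| 1 | 0 | -1 | -1 | 0 |
| 7 | 0 | -7 | -7 | 0 |
| 14 | 0 | -14 | -14 | 0 |
| 28 | 0 | -28 | -28 | 0 |

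The SAP does not say whether 1 day is added to durations. If it is, the fourth column becomes 1, 0, -6, -13, -27 and the last column becomes 1 throughout. The size of the discrepancy does not change.

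**Variant with a later death.** Suppose the same patient withdraws and a death is recorded on day D > 0. Rule 2 drops out because it requires no death. Rule 4 (day -b) now competes with Rule 6 (day D), and min(-b, D) = -b, again before first dose. If two or more assessments had been missed by then, Rule 7 would add a date of 0, and the minimum would still be -b.

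**With the floor:** Rule 4 gives max(-b, 0) = 0. In the main case Rules 2 and 4 then agree for every b. In the variant the earliest date is 0, so the negative value disappears there too.

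**The case against.** **The baseline scan may not be an adequate assessment.** This is the strongest point. The SAP does not define the term, and the protocol, which was not available for this review, may. The text above the table speaks of the last assessment at which the patient was known to be progression-free. Progression is judged against baseline, so baseline is not a natural example. If only post-baseline scans count, Rule 4 has no date for this patient, Rule 2 alone applies, and PFS is 0. This stands as a condition on the finding. Rule 7 points the other way: choosing the later of two dates makes most sense if an adequate assessment can precede first dose. It does not settle the matter, because the clause could also be a fallback for when no adequate scan exists.

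**Rule 2 already gives the right answer.** It does for the surviving patient, and the defect is an overlap between rules rather than a missing rule. But the note resolves overlaps by date, not by specificity, so Rule 2 loses. It does not apply at all in the variant with a later death.

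**Nothing that matters changes.** This largely stands. Section 6.10 says that the study was not designed to assess efficacy, and it specifies no PFS median, Kaplan-Meier estimate, interval or test. Even in an exploratory survival curve, a patient censored at or before day 0 is in no risk set after first dose.

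**A stronger reading that does not hold.** A reader might infer from section 5.1, which extends enrolment if patients discontinue during Cycle 1, that the trial expects such patients, and that one of them would be about 10% of a cohort. The SAP does not support this. Section 5.1 makes a contingent provision to secure complete PK data. Section 6.6 separates stopping treatment from leaving the study, and Rule 4 concerns only loss to follow-up or withdrawal from the study. The figure of 10 per cohort in sections 5.1 and 5.2 is a minimum number of PK completers, not the number treated, so it is not the denominator for such a share.

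**Conclusion.** The point holds in a limited form. As written, Rule 4 and the note together can place a censoring date before the PFS origin. The result is a PFS of -b days instead of 0, where b is the gap from baseline scan to first dose. The range of 0 to -28 days shown above rests on an assumed window.

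Three conditions must be met: the baseline scan counts as an adequate assessment; it precedes first dose (a same-day scan gives 0); and the patient is lost or withdraws from the study before any post-baseline scan. The SAP gives no basis for estimating how many patients, if any, meet the third.

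The consequence is confined to that patient's row in the PFS listing and bar in the swimmer plot. Response rates, OS, safety and PK do not depend on this table. It is an error in a stated rule that is worth correcting, and no threat to the study's conclusions.

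**What to change.** In Table JPBR.6.1, date Rule 4 at the last adequate tumor assessment or first dose, whichever is later, as Rule 7 already does. Patients with a post-baseline scan are unaffected, and Rules 2 and 4 then agree for those without one.

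Restricting Rule 4 to patients with a post-baseline assessment, as Rule 3 is, also works for the surviving patient, who then falls to Rule 2 alone. The two options differ when a death is recorded after withdrawal. With the floor, the note censors that patient at first dose. With the restriction, Rule 4 no longer applies, and the death counts under Rule 6 unless Rule 7 also applies. The sponsor should choose knowingly between them.

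A one-line definition of an adequate assessment, saying whether baseline counts, would remove the remaining ambiguity. The cost is a few words in the SAP table. No data collection or other analysis changes.
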